6. GENERAL CONSIDERATIONS

Continuous variables will be summarized using descriptive statistics such as number of observations (n), mean, standard deviation, median, minimum, and maximum. Categorical variables will be summarized using frequency (n) and percent (%).

The statistical testing will be conducted at a significance level of 0.05 (2-sided) unless specified otherwise. No statistical testing will be conducted for safety measures.

6.1. Adjustments for Covariates

In general, baseline IOP score will be adjusted in the inferential analysis of each IOP endpoint. Detailed information on covariate adjustment is provided in Section 8.1.

6.2. Handling of Missing Data

6.2.1. Efficacy Measure

For each IOP endpoint, no imputation is needed for the MMRM analyses. For sensitivity analysis purpose multiple imputation will be adopted in some analyses.

6.2.2. Safety Measures

Descriptive summaries of safety measures will be based on observed data only. No imputation of missing scores will be implemented.

6.2.3. Dates for Medical Events and Medications

Completely or partially missing onset and resolution dates of medical events, i.e., medical history events and AEs will be imputed in a conservative fashion as follows.

Missing onset dates

- Completely missing: No imputation will be applied.
- Only year is available: Use the first day of the year to impute the missing month and date parts of the onset date
- Year and month are available, but day is missing: Use the first day of the month to impute the missing date part of the onset date.

Missing resolution dates

- Completely missing: No imputation will be applied. The event will be considered ongoing (i.e., not resolved) at the last visit date.
- Only year is available: Use the last day of the year to impute the missing month and date parts of the resolution date
- Year and month are available, but day is missing: Use the last day of the month to impute the missing date part of the resolution date

Same rules will be followed to impute the completely or partially missing start and end dates of non-study medications.

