9.5. Handling of Missing Values

The primary analysis of continuous IOP endpoints will be performed using the MMRM analysis on observed cases. As sensitivity analyses, a PMM approach may be applied to evaluate the impact of missing data on the primary analysis results.

For medical events including AEs and medical history, completely or partially missing onset and resolution dates will be imputed in a conservative fashion to be detailed in the SAP. Similar rules will be followed to impute the completely or partially missing start and end dates of non-study medications.

Unless specified otherwise, descriptive summaries will be based on observed cases.

More details on handling of missing data will be provided in the SAP.

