4.1.3. Treatment Start and End Dates, Extent of Exposure (Days)

Treatment start date is the date at which a randomized subject takes the first dose of the study medication. *Treatment end date* is the date at which a randomized subject takes the last dose of the same study medication. For all treatment arms except the placebo arm, if the date of the last dose is missing, then

- The date prior to Month 3 (Visit 5) will be considered the treatment end date for subjects who completed the study, and
- the date prior to ET visit will be used for subjects who prematurely discontinued the study. If the ET visit date of a non-completer is not available, then the date prior to last available visit date will be considered the treatment end date.

The treatment end date will be set to missing if the treatment start date is missing.

The *extent of exposure* to study medication will be assessed by duration of treatment exposure, derived as:

- Duration of treatment exposure = (Treatment end date – Treatment start date) + 1.

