4.3. Safety-Related Definitions

4.3.1. Adverse Event

Events reported on the AE electronic Case Report Form (eCRF) will be assessed according to the recently amended Food and Drug Administration regulations 21 CFR Parts 312 and 320.

Under Protocol 012601IN, an AE is defined as any untoward medical occurrence that occurs in a study subject, regardless of the suspected cause and regardless of timing of study medication administration. An *on-study* AE can occur any time after the date of informed consent through the last study visit. An AE will be considered as *treatment-emergent* if the AE occurred on or after the treatment start date up to the 2 days (twice the scheduled dosing interval) after treatment end date. Treatment-emergent AEs are a subset of on-study AEs. Both on-study and treatment-emergent AEs will be recorded, but only treatment-emergent AEs will be tabulated.

The severity of each AE will be graded by the Clinical Investigator as Mild, Moderate, or Severe.

Each AE will be classified into a system organ class (SOC) and coded to a preferred term (PT) using Medical Dictionary for Regulatory Activities (MedDRA), version 23.1 published in 2020.

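### An adverse event known only to the month or year of first dose is imputed to before treatment and left out of the treatment-emergent tables

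*SAP*

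**What the plan says.** SAP 6.2.3 gives one set of rules for medical history events and adverse events (AEs), and extends it to non-study medications.

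- Month and year known, day missing: "Use the first day of the month to impute the missing date part of the onset date".
- Year only: "Use the first day of the year to impute the missing month and date parts of the onset date".
- Onset wholly unknown: "Completely missing: No imputation will be applied".
- Resolution with only the day missing: "Use the last day of the month to impute the missing date part of the resolution date".

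None of these refers to first dose. The SAP calls the approach conservative. Protocol 9.5 had promised that "completely or partially missing onset and resolution dates will be imputed in a conservative fashion to be detailed in the SAP".

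SAP 4.3.1 counts an AE as treatment-emergent "if the AE occurred on or after the treatment start date up to the 2 days" after treatment end. On-study AEs are all recorded, "but only treatment-emergent AEs will be tabulated". SAP 4.1.3 defines the treatment start date as "the date at which a randomized subject takes the first dose of the study medication". SAP 9.1 tabulates serious AEs and suspected adverse reactions in the same way as AEs, and provides listings of AEs.

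Two design facts matter. AE collection starts at informed consent, so a date before first dose is a valid on-study date. At Visit 2 subjects are asked about AEs in the clinic (Protocol 8.1.3), and the first dose follows at about 20:00 that evening (Protocol 4.1).

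**The concern.** The imputation rule and the treatment-emergent rule do not work together. Moving an uncertain onset to the start of its month is harmless for medical history. For an AE in the month of first dose, it moves the event across the boundary that decides whether it is tabulated. The events at risk are those that start soon after dosing begins, and they include serious AEs and suspected adverse reactions. Safety is a stated objective, and the tables carry the incidences that readers will use. An AE with no onset date at all gets neither a date nor a treatment-emergent status, so the programmer must decide.

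**Working it through.** The plan gives no figure to reproduce, because this is a date rule. I applied the SAP 4.3.1 test to onsets imputed under SAP 6.2.3.

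**Example.** First dose 15 June, onset known only as June. The imputed onset is 1 June, before treatment start, so the AE is not tabulated. With first dose on 1 June it is kept. With onset known only as July, it is imputed to 1 July and kept.

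**How often the first-dose month is affected.** Of 365 possible first-dose dates in a non-leap year, 12 fall on the first of a month. An AE known only to the first-dose month is kept for 12/365 = 3.3% of start dates and lost for 353/365 = 96.7%. A year-only onset in the first-dose year is kept for 1 of 365 start dates (1 January).

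**Share of month-only on-treatment AEs lost.** Assume first-dose dates uniform over a year and onsets uniform over treatment.

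1. If first dose is on day d of a month with L days, the on-treatment dates in that month number L − d + 1. All are lost if d ≥ 2 and none if d = 1.
2. Summed over d = 2 to L this is L(L − 1)/2: 465 for L = 31, 435 for L = 30, 378 for L = 28.
3. Over the year: 7 × 465 + 4 × 435 + 378 = 5,373. The mean is 5,373/365 = 14.72 lost days per first-dose date.
4. With 90 days of treatment plus the 2-day tail: 14.72/92 = 16.0%.
5. Range over the Month 3 visit window (Day 83 to 97), with or without the tail: 14.72/99 = 14.9% to 14.72/83 = 17.7%.

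The day of first dose matters. In a 31-day month with 92 days at risk:

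| First dose on | Days lost | Share |
|---|---|---|
| 1st | 0 | 0% |
| 2nd | 30 | 32.6% |
| 15th | 17 | 18.5% |
| 31st | 1 | 1.1% |

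**Early events.** For onsets in the first 14 days, the days lost are min(14, L − d + 1) for d ≥ 2. The sums are 329, 315 and 287 for months of 31, 30 and 28 days. The mean is (7 × 329 + 4 × 315 + 287)/365 = 3,850/365 = 10.55 days, and 10.55/14 = 75.3%.

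**What a simple repair would add.** Suppose every AE matching the first-dose month were dated to treatment start. The d − 1 screening dates earlier in that month would then be wrongly counted. Their sum is again L(L − 1)/2 per month, so the mean is 14.72 days with a 35-day screening period. With 28 days the cap removes 25 days over the year: 5,348/365 = 14.65. Days wrongly added would therefore about equal days recovered. As shares of month-only screening AEs, with onsets uniform over screening, these are 14.72/35 = 42.1% and 14.65/28 = 52.3%. If exact resolution dates were recorded, AEs lasted 7 days, and those ending before first dose were excluded, the shares would fall to 15.2% and 19.0%, about 5.3 days in either case.

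**The case against.** **Few events are affected, and none is lost from the record.** This stands as a limit on size. AEs are queried at Weeks 2 and 6, Month 3 and the follow-up call. The protocol asks for event dates, and eCRFs are due within 3 business days where possible. Year-only onsets are unlikely under that schedule. Safety is descriptive, and the AE listings in SAP 9.1 retain every event. None of this corrects the classification that the rule produces.

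**Conservative is not defined.** Earliest onset with latest resolution maximises duration, which is one coherent meaning. A reader might infer that the plan flatly contradicts itself, but the documents do not support that. They support only that the rule is not conservative for treatment-emergent status.

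**Stronger readings to avoid.** A reader might take 16% or 75% as a share of all AEs. Both are shares of month-only AEs, and the documents give no count of these. A reader might also infer that the rule favours DE-126. It applies equally to both arms, and nothing shows that partial dates are commoner in one.

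**A repair can misclassify in the other direction.** This also stands. An AE already reported at Visit 1, 1a or 2 is known to precede the first dose, and a rule that looks only at the resolution date would relabel it if it were ongoing. The fix below therefore uses the time of first report.

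**Conclusion.** The defect is real and narrow. Followed as written, the SAP classes an AE known only to the month or year of first dose as pre-treatment and omits it from the tables, unless dosing began on day 1 of that period. No other passage corrects this. Under the uniform assumptions above, about 16% of month-only on-treatment AEs are lost (14.9% to 17.7%), and about 75% of those starting in the first 14 days. Onsets known to a later month are not lost in this way. The absolute number cannot be estimated and is probably small. It is worth correcting before unmasking because the rule acts against early events and the repair is cheap. It is not a threat to the trial's conclusions on what the documents show.

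**What to change.** In SAP 6.2.3, for AEs only:

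- If the known part of the onset date (month and year, or year alone) matches first dose, impute the treatment start date, unless **(a)** the AE was already recorded at or before the Visit 2 AE query, or **(b)** a recorded, not imputed, part of the resolution date shows that it ended before first dose. Otherwise keep the present rule.
- Treat an AE with a completely missing onset as treatment-emergent unless (a) or (b) applies.
- Leave the rule for medical history and medications as it is.

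Condition (b) must use recorded parts only. A resolution imputed to month-end can never fall before a first dose in the same month.

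**Cost.** SAP wording and one derivation. Condition (a) needs the visit or date of first report. Protocol 8.6.1.3 and Appendix E do not list this as an AE item, so its availability in the database should be confirmed. Some screening AEs with partial dates will still be counted as treatment-emergent. The exclusions bring this below the roughly 14.7 days per first-dose date shown above, and over-inclusion is the conservative direction for safety tables.

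Two separate minor points can be settled in the same revision:

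- Protocol 8.6.5 includes AEs that worsen after first dose in its treatment-emergent definition, and SAP 4.3.1 does not. Aligning them needs a new AE record or a dated severity change, because Protocol 8.6.1.3 lists maximum severity but no date of worsening.
- Protocol 8.6.1.3 and 8.6.5 end AE collection at withdrawal or the exit visit, while footnote d of Protocol Table 3 and SAP Table 1 runs to 2 weeks after last dose. For completers the 2-day window means little effect on the tables, but the passages should be reconciled.

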6.3. Multi-Center Studies

This is a multi-center study. The number of subjects enrolled from each site will not be pooled in this study.

6.4. Multiple Comparisons / Multiplicity

Fixed sequence procedure will be applied to control the overall Type I error rate across the four hypotheses in the primary and key secondary endpoints at the 0.05 level. Fixed sequence procedure tests hierarchically ordered hypotheses at level 0.05 until the first non-rejection.

The fixed sequence for the four hypotheses in this study is as follows:

1. Hypothesis of non-inferiority of DE-126 ophthalmic solution 0.002% to Timolol maleate ophthalmic solution 0.5% for the primary endpoint, IOP at each scheduled timepoint (08:00, 10:00, and 16:00) at Week 2, Week 6, and Month 3.
2. Hypothesis of non-inferiority of DE-126 ophthalmic solution 0.002% to Timolol maleate ophthalmic solution 0.5% for the key secondary endpoint, mean diurnal IOP at Month 3.
3. Hypothesis of superiority of DE-126 ophthalmic solution 0.002% to Timolol maleate ophthalmic solution 0.5% for the key secondary endpoint, mean diurnal IOP at Month 3.
4. Hypothesis of superiority of DE-126 ophthalmic solution 0.002% to Timolol maleate ophthalmic solution 0.5% for the primary endpoint, IOP at each scheduled timepoint (08:00, 10:00, and 16:00) at Week 2, Week 6, and Month 3.

6.5. Interim Analysis

No formal interim analysis is planned for this study.

7. SUMMARY OF STUDY POPULATION DATA

7.1. Subject Disposition

The disposition of all randomized subjects will be summarized by treatment and overall. The summary will include the number of subjects in the FAS population the Safety population, and the PP population. The disposition summary will also include the number and percentage of completers and non-completers at Month 3 (Visit 5), by the primary discontinuation reason.

7.2. Demographics and Baseline Characteristics

Subject demographics and baseline characteristics will be descriptively summarized for the FAS population by planned treatment, Safety population by actual treatment, and overall. Specifically, for subject demographics, the following variables will be summarized:

- Age at randomization (continuous and categorical: < 65 years or \geq 65 years)
- Sex (categorical: Male or Female)
- Race (categorical: Asian, Black or Africa American, or White)

For baseline characteristics, the following variables will be summarized for study eye and fellow eye separately:

- Baseline mean diurnal IOP in the study eye: <25 mmHg vs. \geq 25 mmHg.
- Primary ocular diagnosis (categorical: POAG or OHT)
- Prior use of IOP-lowering medication(s) (categorical: β -adrenergic antagonist, prostamide or prostaglandin analogue, α -adrenergic agonist, carbonic anhydrase inhibitors, miotic agent, ROCK inhibitor, other, or none)
- Prostaglandin naive (Yes or No)
- Baseline lens status (categorical: phakic or pseudophakic/aphakic)
- Baseline mean diurnal IOP score and baseline IOP score at each scheduled timepoint (08:00, 10:00, and 16:00)
- BCVA (logMAR)
- Baseline central corneal thickness
- Glaucomatous optic nerve findings (categorical: none, mild, moderate, or severe)
- Baseline glaucoma hemifield test result by device (categorical: within normal limits, borderline, or outside normal limits)
- Baseline visual field global indices by device
 - mean deviation
 - pattern standard deviation

7.3. Medical and Surgical History

For this study, medical and surgical history (i.e., medical events) will be coded using MedDRA [23.1, 2020](#). Each medical event will be classified into a SOC and mapped to a PT.

The medical and surgical history will be summarized for the FAS population. Subjects reporting any medical and surgical history at baseline will be tabulated by SOC and PT for each planned treatment and overall.

Baseline lens status (categorical: phakic or pseudophakic/aphakic)

7.4. Protocol Deviations

In this study, protocol deviations are categorized as follows:

- Informed consent
- Inclusion/exclusion criteria
- Concomitant treatment
- Investigational product
- Procedures/tests/assessments
- Laboratory
- Randomization
- Safety issues
- Time Window
- Protocol implementation issues
- Other deviations

A protocol deviation is considered major if it may affect the subject's rights, safety, or well-being and/or the completeness, accuracy, and reliability of the study data. Santen's study team will review all protocol deviations and determine the list of major protocol deviations prior to database lock. All randomized subjects with any major protocol deviation(s) will be tabulated by deviation category for each planned treatment and overall.

7.5. Prior and Concomitant Medications

For this study, non-study medications, including prior and concomitant medications, will be coded using World Health Organization Drug Dictionary Enhanced (WHO-DDE) (March 2017). Each non-study medication will be classified using the Anatomical-Therapeutic-Chemical (ATC) classification system and mapped to a WHO-DDE preferred drug name.

Non-study medications will be summarized for the Safety population. Subjects taking any prior medications will be tabulated by ATC level 3, level 4 and preferred drug name for each actual treatment received and overall. A subject will be counted at most once for each prior medication, even if the subject took the same prior medication on multiple occasions. Subjects taking any concomitant medications will be tabulated similarly. In addition, prior medications and concomitant medications will also be listed, separately.

7.6. Treatment Compliance

A subject will be considered fully compliant to treatment if he/she responded “0” at all post-baseline visits to the eCRF question “How many doses were missed since the previous visit?”

The treatment compliance rate for a subject at a visit will be as following.

Treatment Compliance Rate (%)

$$\begin{aligned}
 &= \frac{(\text{Duration} - \text{Total Number of Missed Dose})}{\text{Duration}} \times 100 && \text{if the subject did not withdraw the} \\
 &&& \text{study medication before this visit} \\
 &= \frac{\text{Duration} - \text{Total Number of Missed Dose} - (\text{Current Visit Date} - \text{Treatment End Date})}{\text{Duration}} \times 100 \\
 &&& \text{if the subject withdrew the study medication before this visit,}
 \end{aligned}$$

where

- duration is the number of days subjects should have administered study medication, calculated as current visit date – baseline date, and
- total number of missed dose is the total number of days that subject did not follow the proper dosing procedures or dosing schedule since baseline.

For FAS subjects, treatment compliance will be summarized by post-baseline analysis visit for each planned treatment and overall.

7.7. Exposure to Study Medication

The duration of exposure to a study medication is measured by days on treatment as derived in [Section 4.1.3](#). For Safety subjects, the duration of exposure will be summarized using descriptive statistics for actual treatment received and overall. Frequency and percentage of subjects will also be tabulated by analysis visit.

8. EFFICACY ANALYSES

Unless specified otherwise, the efficacy analyses will be performed on the FAS, where subjects are classified by planned treatment, irrespective of the actual treatment received.

Unless specified otherwise, all efficacy analyses will be performed on the study eye, and the data on fellow eye will not be used.

8.1. Analyses of Primary Endpoint and Key Secondary Endpoint

8.1.1. Primary Analysis

8.1.1.1. Primary Endpoint

The primary efficacy endpoint is the IOP in the study eye at each scheduled timepoint (08:00, 10:00, and 16:00) at each of three follow-up visits, Week 2, Week 6, and Month 3. The nine combinations of three scheduled timepoints at each of three visits are referred to subsequently as nine timepoints. For the primary endpoint, the following hypotheses will be tested:

$$H_0: \mu_T - \mu_C > \Delta \text{ for at least one timepoint}$$

versus

$$H_A: \mu_T - \mu_C \leq \Delta \text{ at all nine timepoints}$$

where μ_T and μ_C denote the mean values of the primary endpoint in the DE-126 arm and the Timolol arm, respectively, and Δ denotes the noninferiority margin of 1.5 mmHg.

The primary analysis of the primary efficacy endpoint will be performed using a MMRM based on the FAS. A separate MMRM will be used for IOP at each scheduled timepoint (8:00, 10:00, or 16:00). For each scheduled k th timepoint, the model will include treatment (T_i), analysis visit (V_j), and treatment-by-visit interaction (TV_{ij}) as fixed effects, and the baseline IOP (B_k) as covariates:

$$IOP_{ijkn} = \mu + T_i + V_j + TV_{ij} + B_k + \varepsilon_{ijkn}$$

where μ denotes the overall mean, and ε denotes the random error associated with the individual subject. The above model allows treatment effect and its variability to vary over study visits.

Correlations of IOP measurements within-subject will be modeled using an unstructured covariance matrix. If there are convergence issues, covariance matrix structures other than unstructured will be tried in the following order: (1) heterogeneous Toeplitz (TOEPH), (2) heterogeneous autoregressive of order 1 (ARH(1)), (3) heterogeneous compound symmetry (CSH), and (4) compound symmetry (CS). The first covariance structure that converges will be used as the primary analysis. Least squares mean IOP values for each treatment arm and differences between least squares treatment arm means and associated 95% confidence intervals will be reported for each of the nine timepoints.

For the subjects who receive IOP-lowering rescue therapy, any IOP values collected after the receipt of rescue therapy will be censored (i.e., treated as missing) in the analyses.

Noninferiority criteria for primary endpoint: With respect to the primary study objective, noninferiority of DE-126 to Timolol is established if the upper limit of the two-sided 95% confidence interval for the difference in the mean IOP (DE-126 minus Timolol) is ≤ 1.5 mmHg at all nine timepoints and ≤ 1.0 mmHg in majority (five or more) of the nine timepoints.

Superiority of DE-126 to Timolol for the primary efficacy endpoint will be claimed if the upper limit of the two-sided 95% confidence interval for the difference in the mean IOP (DE-126 minus Timolol) is < 0 mmHg at all nine timepoints.

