3.2. Randomization and Masking

A stratified permuted-block randomization will be employed to randomize eligible subjects in a 1:1 ratio to either DE-126/Vehicle arm or Timolol Maleate arm. The randomization will be stratified by mean diurnal IOP in the study eye at baseline visit (Visit 2): <25 mmHg vs. \geq 25 mmHg.

The randomization schedule will be generated and implemented using central randomization via Interactive Response Technology (Medidata Rave RTSM). Each randomized subject will receive numbered study medication kits as assigned by Medidata Rave RTSM (Randomization and Trial Supply Management system).

This is a double-masked study. The subjects, Investigators, Examiners, and Santen personnel involved in the conduct of the study will be masked to the study treatment. An authorized unmasked study staff member at the investigative site who is not the Investigator or Examiner will dispense and collect study medication(s) and will query about dosing compliance.

Subjects will be instructed not to show the eye drop bottles or discuss the eye drops to either the Investigator or the Examiner or other study subjects. The active control treatment (Timolol Maleate) bottles will be over-labeled and packaged in the same secondary package (e.g., cardboard carton) as the investigational treatment (DE-126). Subjects in DE-126/Vehicle arm will receive a kit containing 2 bottles labeled “morning” for the morning dose and 2 bottles labeled “evening” for the evening dose. Subjects on Timolol arm will receive a kit containing 2 bottles labeled morning/evening for the BID dosing.

Each eligible subject will receive a numbered study medication kit assigned by Central randomization via Interactive Response Technology (Medidata Rave RTSM) at Visit 2 (Baseline, Day 1) and at Visit 4 (Week 6).

In case of a medical emergency, the Principal Investigator may reveal the treatment information by unmasking through Medidata Rave RTSM to know which treatment the subject has received. The Principal Investigator (or his/her designee) should contact Santen, or Santen’s designee, before taking this measure, if there is sufficient time. Santen, or Santen’s designee, must be informed of all instances where the code is broken and of the reasons for such instances.

Additionally, the AE or SAE for which study treatment was unmasked should be reported to Santen Pharmacovigilance.

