4.2.2. Efficacy Measure

IOP (in mmHg) is the efficacy measure for this study. For the IOP at each timepoint of measurement, a mean of two consecutive measurements using the Goldmann applanation tonometer will be used. If the two measurements differ by 3 mmHg or more, then a third measurement will be made, and the median of the three consecutive measurements will be used.

The mean diurnal IOP at each visit is defined as the mean of the three scheduled timepoints 8:00, 10:00, and 16:00 at the visit. If there are one or more missing IOP measurement at timepoints, the mean diurnal IOP will not be calculated.

To assess the efficacy of DE-126, the mean/median IOP at each scheduled timepoint (8:00, 10:00, 16:00) and the mean diurnal IOP in the study eye will be analyzed. In addition, changes and percent changes from baseline in IOP at each timepoint and the mean diurnal IOP in the study eye will also be analyzed.

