8.1.1.2. Key Secondary Endpoint

The key secondary efficacy endpoint is the mean diurnal IOP in the study eye at Month 3. The following null (versus alternative) hypothesis will be tested:

$$H_{0S}: \mu_{TM} - \mu_{CM} > \Delta \quad \text{vs.} \quad H_{AS}: \mu_{TM} - \mu_{CM} \leq \Delta$$

where μ_{TM} and μ_{CM} denote the mean diurnal IOP at Month 3 of the DE-126 and Timolol arm, respectively, and Δ denotes the noninferiority margin of 1.5 mmHg. The primary analysis of this key secondary efficacy endpoint will be performed using a MMRM based on the FAS. The model will include treatment, analysis visit (Week 2, Week 6, or Month 3), and treatment-by-visit interaction as fixed effects, and baseline mean diurnal IOP as a covariate. Correlations of mean diurnal IOPs within-subject will be modeled using an unstructured covariance matrix. The mathematical model is analogous to the model in the primary efficacy endpoint.

If there are convergence issues, covariance matrix structures other than unstructured will be tried in the following order: (1) heterogeneous Toeplitz (TOEPH), (2) heterogeneous autoregressive of order 1 (ARH(1)), (3) heterogeneous compound symmetry (CSH), and (4) compound symmetry (CS). The first covariance structure that converges will be used as the primary analysis. Least squares mean diurnal IOP values at Month 3 for each treatment arm and the difference between least squares treatment group means and its 95% confidence interval will be reported.

Noninferiority of DE-126 to Timolol is achieved for this endpoint if the upper limit of the 95% confidence interval for the difference between DE-126 and Timolol (DE 126 minus Timolol) in the mean diurnal IOP at Month 3 is ≤ 1.5 mmHg. Superiority of DE-126 to Timolol is achieved for this endpoint if the upper limit of the 95% confidence interval is < 0 mmHg.

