8.2. Analyses of Other Secondary Endpoints

For continuous secondary endpoints (IOP, mean diurnal IOP, change and percent change from baseline in IOP/mean diurnal IOP) at Week 2, Week 6 and Month 3, both MMRM and descriptive summaries will be performed. The MMRM will be the same as the one for key secondary endpoint but without multiplicity adjustment.

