8.3. Subgroup Analyses

To assess the homogeneity of treatment effects among subgroups, descriptive summaries for all IOP endpoints will be conducted by the following categories:

- age group (< 65, or \geq 65 years)
- sex (males or females)

- race (White or non-White)
- mean diurnal IOP in the study eye at baseline visit (<25 mmHg vs. \geq 25 mmHg)
- primary ocular diagnosis (primary open-angle glaucoma or ocular hypertension).

If there are a sufficient number of subjects in each subgroup, the test of interaction will be conducted using an MMRM with treatment, visit, treatment-by-visit, subgroup, and treatment-by-subgroup as fixed effects, baseline IOP score (score at the corresponding timepoint or mean diurnal score) as a covariate, and subject as a random effect.

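### The primary model is valid but leaves out baseline mean diurnal IOP, the variable randomisation is stratified on; the protocol and SAP also name different main responder tests

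*SAP*

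**What the plan says.** **Primary model.** SAP 8.1.1.1 uses a separate MMRM for 08:00, 10:00 and 16:00. Each has treatment, visit and treatment-by-visit "as fixed effects, and the baseline IOP (B_k) as covariates". B_k is the study-eye baseline at the same hour as the outcome.

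**Stratification.** SAP 3.2 states: "The randomization will be stratified by mean diurnal IOP in the study eye at baseline visit (Visit 2". The two levels are below 25 mmHg and 25 mmHg or above. Neither the continuous mean nor its category is in the primary model.

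**Decision rule.** Non-inferiority requires an upper 95% limit that "is ≤ 1.5 mmHg at all nine timepoints and ≤ 1.0 mmHg in majority (five or more) of the nine timepoints".

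**Where the mean is used.** The key secondary model in SAP 8.1.1.2 has "treatment-by-visit interaction as fixed effects, and baseline mean diurnal IOP as a covariate". SAP 8.2 then says, for the other continuous endpoints, "The MMRM will be the same as the one for key secondary endpoint but without multiplicity adjustment". SAP 8.3 words the covariate more carefully: "baseline IOP score (score at the corresponding timepoint or mean diurnal score) as a covariate".

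**Responders.** Protocol 9.7.2.2 analyses the binary endpoints by Pearson chi-square and allows Fisher's exact test as a sensitivity analysis. SAP 8.2.1 names Fisher's exact test and does not mention chi-square. Both tests ignore the randomisation stratum.

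**The concern.** The primary rule is a conjunction over nine intervals, so its power depends directly on the standard error. Planned power is only 70% (SAP 3.3). A prognostic baseline variable that is already collected, used to stratify, and trusted in the key secondary model is absent from the primary one. What is at stake is precision.

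For responders, two governing documents name different main tests for four endpoints at three visits. If this is not settled before unmasking, the choice could be questioned afterwards, and the test that the SAP names is the conservative one.

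**Working it through.** **1. The plan's own power figure.** Inputs from SAP 3.3: SD 4.0 mmHg, 140 per arm, true difference 0, margin 1.5 mmHg, two-sided 5%, correlation 0.6.
- SE = 4.0 × √(2/140) = 0.478 mmHg.
- One timepoint: Φ(1.5/0.478 − 1.96) = Φ(1.18), about 88%.
- Nine equicorrelated differences (0.6), no covariate, by simulation: all nine limits ≤1.5 mmHg, 61%; full rule, 51%.
- Sample size: 280 × 1.05 = 294, as stated.

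The 70% is not reproduced from the stated inputs. The full rule reaches about 70% if the residual SD is near 3.4 mmHg, which is compatible with some baseline adjustment that the documents do not describe. Only power gains are used below, not absolute levels.

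**2. Validity without the mean.** In 6,000 simulated trials with stratified blocks and a true difference at the 1.5 mmHg margin (one visit), B_k alone gave bias −0.005 mmHg and one-sided error 2.5%. Adding the mean gave 2.7%, within simulation error. Average model SE was 0.404 with B_k, 0.402 with B_k plus the two-level stratum, and 0.395 with B_k plus the continuous mean. The category adds little; the continuous mean adds more.

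**3. Why the mean can help.** Suppose each baseline hour correlates r with the outcome and the baseline hours correlate c with each other. Residual SD is 4√(1 − r²) with B_k, and 4√(1 − r²/[(1 + 2c)/3]) with the mean. With r = 0.3 and c = 0.6 this is 3.82 against 3.75. With r = 0.5 and c = 0.6 it is 3.46 against 3.25. This ignores the entry range, which weakens baseline correlations and makes small gains more plausible.

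**4. Full-rule power within the entry range.** All inputs other than SD and sample size are assumptions: three baseline and nine post-baseline readings jointly normal, baseline limited to 22–34 mmHg at all three hours (protocol 5.1, criterion 11), means before that limit 25.5/24.5/23.5, post-baseline SD 4.0, 140 per arm, difference 0, complete data, 300,000 draws.

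| Correlation: same day / matched hour, other day / different hour, other day | B_k | B_k + mean | Gain |
|---|---|---|---|
| 0.6 / 0.6 / 0.6 | 50.0% | 62.0% | 12.0 |
| 0.5 / 0.5 / 0.5 | 44.4% | 52.6% | 8.2 |
| 0.8 / 0.6 / 0.6 | 55.5% | 60.9% | 5.4 |
| 0.8 / 0.5 / 0.5 | 51.5% | 54.6% | 3.1 |
| 0.7 / 0.4 / 0.4 | 46.6% | 49.2% | 2.6 |
| 0.7 / 0.5 / 0.45 | 50.6% | 52.5% | 1.9 |
| 0.8 / 0.6 / 0.55 | 58.0% | 59.7% | 1.7 |
| 0.75 / 0.6 / 0.5 | 58.7% | 59.4% | 0.7 |
| 0.8 / 0.6 / 0.5 | 60.5% | 60.6% | 0.1 |

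The Monte Carlo standard error is about √(0.6 × 0.4/300,000) = 0.09 points per entry, so the last row is no gain. In the last four rows the matched hour correlates best. The SE falls by 0.1% to 6.5% over the table. Replacing B_k by the mean loses power in the last two rows (58.7 to 56.3 and 60.5 to 56.9), so the mean should be added to B_k and not substituted for it.

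**5. Responder tests.** Exact enumeration at 140 per arm, true rates 20% to 80%: size 3.5% to 3.7% for Fisher and 4.8% to 5.1% for chi-square. The next table gives power in 6,000 simulated trials per scenario (assumed: control post-treatment mean 18.5 mmHg, shift −1.0, central baseline mean 24.5), as Fisher / chi-square / Cochran-Mantel-Haenszel (CMH) by stratum.

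| Endpoint | Same-day 0.8, cross-day 0.6 | Same-day 0.7, cross-day 0.4 |
|---|---|---|
| ≤18 mmHg | 39.2 / 43.0 / 47.9 | 42.4 / 46.0 / 47.4 |
| ≥20% | 34.4 / 40.2 / 40.3 | 31.9 / 36.8 / 36.9 |
| ≥25% | 46.4 / 51.0 / 50.9 | 42.3 / 45.5 / 45.5 |
| ≥30% | 50.2 / 53.6 / 53.7 | 46.5 / 50.0 / 49.8 |

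Leaving Fisher for chi-square gains 3.2 (45.5 − 42.3) to 5.8 points (40.2 − 34.4). Stratifying then adds 1.4 to 4.9 points for ≤18 mmHg and −0.2 to +0.1 for the percent reductions.

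**The case against.** **The model is sound as written.** Pairing each outcome with its own baseline follows SAP 6.1 and 8.3, and the gain rests on correlations the documents do not give. This stands. A reader might infer that omitting the stratification variable biases the analysis or inflates type I error. It does not: B_k is one of the three readings in the mean, and the simulated error is nominal.

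**The covariate is not automatically complete.** It is tempting to say that criterion 11 guarantees it for every eligible subject. SAP 4.1.7 ends the 08:00 analysis window at 8:59, whereas the permitted window runs to 9:00, and it does not say whether baseline is exempt. A permitted 08:00 reading finishing at 9:00 could map to 10:00, and SAP 4.2.2 then says: "If there are one or more missing IOP measurement at timepoints, the mean diurnal IOP will not be calculated". With B_k alone that subject leaves one model; with the mean added, all three. Where the SE cut is only 0.1%, losing about 0.2% of 280 subjects (fewer than one) cancels the gain. This stands, and the fix must cover it.

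**SAP 8.2 is largely answered elsewhere.** Read literally, it would fit the mean diurnal covariate to clock-time outcomes and produce a second set of the nine differences. SAP 4.2.3, 6.1 and 8.3 point to each endpoint's own baseline, and SAP 2.2.3 lists change and percent change, not IOP itself, as the clock-time secondary endpoints. No decision rule attaches to them. Only a wording point remains.

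**The responder conflict is small.** Protocol section 9 defers detail to the SAP, and SAP section 1 makes the SAP the basis of the study report, so Fisher would probably be used. These endpoints lie outside the fixed sequence (SAP 6.4). The mismatch is nevertheless real, and Fisher's conservatism does not depend on the assumed correlations.

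**Conclusion.** The point holds as a matter of precision and consistency. The primary analysis is valid; adding baseline mean diurnal IOP to B_k is worth about 0 to 2 points of full-rule power if the matched hour is the most informative, and up to about 12 if all hours are equally informative. No structure tested showed a loss beyond simulation error. These figures rest on assumed correlations, normality, SD 4.0 mmHg and complete data.

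The responder-test mismatch is a plain conflict of text. Leaving Fisher gains roughly 3 to 6 points in the scenarios shown. The stratum matters only for ≤18 mmHg, where its share can be as large as that of leaving Fisher. No confirmatory claim is affected.

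**What to change.** 1. **SAP 8.1.1.1:** add continuous baseline mean diurnal IOP alongside B_k in each clock-time model. Derive it from the scheduled Visit 2 readings used for eligibility and stratification, and state that the SAP 4.1.7 windows do not apply to that derivation. Cost: 1 degree of freedom per model and no new data.
2. **Protocol 9.7.2.2 and SAP 8.2.1:** name the same main responder test before unmasking. A CMH test stratified by <25 / ≥25 mmHg, with a Mantel-Haenszel risk difference and 95% CI, is preferable; keep Fisher as a sensitivity analysis. Cost: one sentence in each document.
3. **SAP 8.2 (minor):** say that clock-time endpoints use the same covariates as the primary model. IOP and change from baseline at the same hour then give identical treatment differences. Cost: one clause.
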